A total of one hundred participants will be recruited from the University of North Carolina (UNC) School of Dentistry (SOD) Graduate Prosthodontics clinic, Graduate Operative clinic, and the Dental Faculty Practice. A stratified block randomization will be used to randomize patient to impression technique: Aquasil Ultra Cordless, Dentsply International using Aquasil Ultra Polyvinyl siloxane (PVS) impression material versus Dentsply International, gingival displacement cord (Ultrapak, Ultradent Products International) hydrated with aluminum chloride hexahydrate (Hemodent, Premier Dental Products Company). Stratification will be based on the clinic where treatment is provided (Dental Faculty Practice, Graduate Operative Dentistry, Graduate Prosthodontic Clinic). A block size of 4 within each stratum will be used to maintain a balanced allocation to impression group. The randomization schedule will be prepared by [name]. Randomization allocations will be placed in sequentially numbered envelopes for ease of use by clinicians within the three clinics.

The treating clinician will open the allocation envelope after the tooth preparation is completed. This is to limit the potential bias of the clinician altering the tooth preparation design in anticipation of a known gingival displacement technique. Although the patient may require restorations on multiple teeth, only one tooth, the most posterior, will be included in the evaluation. The clinician will be instructed to

complete the impression for that tooth before proceeding to other teeth. The patient will be informed that participation, if multiple teeth are treatment planned, may increase the appointment time.

The gingival displacement procedures and impression procedures are described here:

Traditional Corded Impression Procedure:

- 1) The prepared tooth is washed and dried, and assure hemostasis.

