- Patients must have read, understood and signed an informed consent form.
- Patients must be in good general health, (based on a review of the medical history, blood pressure and heart rate).
- Patients must have no health-related contra-indications to dental treatment.
- Patient must require at least one indirect restorations (crowns).
- Probing pocket depths around the treatment tooth/teeth must be 4mm or less.
- There must be no bleeding on probing around the treatment tooth/teeth.
- The prepared finish line must be between 0 to 1mm sub-gingival (inclusive).

Exclusion Criteria:

- Individuals who have a chronic disease with oral manifestations.
- Individuals who exhibit gross oral pathology.
- Smokers
- Uncontrolled Diabetics (per review of medical history)
- Probing pocket depths around treatment tooth/teeth of greater than 4mm.
- Bleeding on probing around treatment tooth.teeth.
- The prepared finsh line is greater than 1mm sub-gingival.

The inclusion/exclusion criteria limit generalizability of the findings to patients without confounding periodontal or medical issues. However, the sample size of this study is not sufficient to extend to a consideration of the effect of these confounders on the comparison of the two impression techniques.

The proposed research study requires a total of 100 participants. Patients will be recruited from and will be treated in the Dental Faculty Practice, the Graduate Operative Clinic, and the Graduate Prosthodontic Clinic. The patient may seek other dental treatments in the above mentioned clinics or in other clinics in the School of Dentistry.

Study clinicians will be trained and calibrated on both the cordless and the corded gingival displacement procedures and impression procedures in a practice session. Clinical instruction protocols will be printed on laminated forms for all study clinicians to follow, for both the cordless and the corded procedures. These clinical protocol forms will be in the clinicians operatory during actual study treatment, and this protocol must be followed for the impression to be included in the study. The clinical instruction protocol is listed in Appendix A.

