In addition to a signed Consent form, the study subject will be asked to complete the standard adult medical and dental health history questionnaire provided by the UNC SOD (Appendix 1) and will be provided with the UNC Chapel Hill Notice of Privacy Practices and the Consent for Purposes of Treatment, Payment and Health Care Operations (Appendix 2). Other than the research consent, these are standard practices followed by UNC SOD for all patients. The study is mandated to adhere to these protocols prior to treating a patient at the UNC SOD. After consent has been obtained, an oral examination will be performed by the treating dentist to confirm the patient meets inclusion criteria. The patient will be dropped from the study if inclusion/exclusion criteria are not met. The treating clinician will record the criteria that resulted in the patient being dropped (See Appendix B). If the inclusion criteria are not met, a clinically appropriate impression method will be performed at the clinician's judgment and will be made per case by the treating clinician, following standard of care.

Customary anesthesia and tooth preparation will be performed by the clinician as necessary for the particular indirect restoration. The gingival displacement procedure and impression will be made as described in this study protocol and as followed on the laminated clinical protocol sheet. If the clinician finds that the first impression is inadequate and chooses to make an additional impression, only the first impression will be evaluated for the study and a note will be indicated to record the number of impressions the clinician made to achieve an acceptable impression.

Patients will be given appropriate verbal and written post-procedure instructions; and appointments will be made for restoration try-in and delivery, as would happen as part of their regular treatment.

There are no potential direct benefits to the participant besides the fact that particularly close attention will be paid to the gingival displacement and impression procedures, and there will be close evaluation of impressions.

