GingiBraid retraction cord	12 containers- sizes: 00,0,1,2; (3) of each.	Included in normal clinic treatment
Hemodent	3 bottles + 1 for practice calibration	Included in normal clinic treatment
Viscostat	60 disposable vial/syringe	Included in normal clinic treatment
Impression trays	60 trays + 20 for practice calibration	Included in normal clinic treatment
Impression tray adhesive	3 bottles + 1 for practice calibration	Included in normal clinic treatment
Estimate Total:		

Timeline

The study is planned to last approximately 1.5 years to allow for recruitment and data collection and analysis. The study would ask the participants to come to 2 appointments; it might be possible to consent the patient and perform treatment on the same day, if the patient was scheduled for treatment that day already.

TO BE COMPLETED BY TREATING CLINICIAN:

Patient did not meet inclusion/exclusion criteria and is dropped from the study

Medical/smoking

Probing pocket depths around treatment tooth/teeth of greater than 4mm.

Bleeding on probing around treatment tooth/teeth.

The prepared finish line is greater than 1mm sub-gingival

Patient meets inclusion/exclusion criteria

Patient ID: _____

Impression Group: _____ *Corded* _____ *Cordless*

Clinic: _____ *Dental Faculty Practice*

_____ *Graduate Operative Clinic* _____ *1st* _____ *2nd* _____ *3rd*

_____ *Graduate Prosthodontic Clinic* _____ *1st* _____ *2nd* _____ *3rd*

Patient Age: _____

Gender: _____ *Male* _____ *Female*

Type of impression material used:

Tray adhesive used:

Aquasil Ultra Cordless

Aquasil Ultra

Yes *No*

Tray material:

Metal stock *Plastic stock* *Custom* *Plastic dual arch* *Metal dual arch*

Type of tray used:

Ant quad *Post quad* *Full arch*

Number of units requested:

2-3 FDP *Onlay* *Single crown x _____*

Anterior *Canine* *Premolar* *Molar*

Jaw: *Maxillary* *Mandibular*

Time Required for 1st Impression: _____ minutes and seconds

Number of Impressions Required to Obtain Adequate Impression: _____

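### Finish-line eligibility can be judged only after preparation, by the clinician who opens the envelope, and nothing requires that decision to come before the arm is seen

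*Combined protocol and SAP*

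**What the plan says.** All references are to the combined protocol and SAP.

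- **Eligibility examination (Methods).** "After consent has been obtained, an oral examination will be performed by the treating dentist to confirm the patient meets inclusion criteria". The next sentence is "The patient will be dropped from the study if inclusion/exclusion criteria are not met". A dropped patient then receives an impression method of the clinician's choosing.
- **Preparation (Methods, next paragraph).** "Customary anesthesia and tooth preparation will be performed by the clinician as necessary for the particular indirect restoration".
- **Finish-line criterion.** Inclusion Criteria require a prepared finish line 0 to 1 mm below the gingiva, and Exclusion Criteria repeat the upper limit. The treating clinician's form offers it as a reason for dropping: "The prepared finish line is greater than 1mm sub-gingival".
- **Allocation (Methods, randomization).** "The treating clinician will open the allocation envelope after the tooth preparation is completed". The reason given is: "This is to limit the potential bias of the clinician altering the tooth preparation design in anticipation of a known gingival displacement technique". Eligibility is not mentioned there.
- **Technique compliance (Methods, clinician training).** An impression counts in the study only if the laminated protocol was followed.
- **Analysis (Statistical Analysis).** No analysis population is defined, and no rule covers a patient dropped after the envelope is opened.

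**The concern.** Delaying the envelope until preparation is complete protects the preparation from knowledge of the arm. That protection does not extend to the eligibility decision, which for the finish line falls in the same interval and to the same person. A 1 mm limit leaves room for judgment. A clinician who has seen the allocation could, without bad intent, call a borderline tooth ineligible and then use whichever technique seems suitable.

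If such drops depend on the arm and the dropped teeth are the harder ones, the remaining groups are no longer the randomized groups. All three primary outcomes (errors, time, discomfort) are exposed. The technique-compliance rule opens a second route, because whether a protocol was followed is known only after allocation and may differ between techniques.

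**Working it through.** **1. The plan's own figure.** For 80% power at P = 0.709, two-sided 0.05, Noether's formula gives

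N = (1.960 + 0.842)² / [12 × 0.5 × 0.5 × (0.709 − 0.5)²] = 7.849 / 0.1310 = 59.9 in total,

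that is 29.95, or 30 per arm, as stated. The point does not depend on this figure. The illustration below uses the recruitment target of 100, so 50 per arm.

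**2. The sequence.**

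| Step | Who | Is the finish line observable? | Is the arm known? |
|---|---|---|---|
| Oral examination, drop rule | Treating dentist | No | No |
| Anesthesia and preparation | Treating clinician | Only at the end | No |
| Finish-line judgment | Treating clinician (form) | Yes | Not specified |
| Envelope opened | Treating clinician | Yes | Yes from here |

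The third row is the gap. The text fixes the envelope after preparation, but it does not fix the finish-line judgment before the envelope.

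**3. Size if the gap were used.** Every input here is an assumption, since the documents give none of them. There is no true difference. A share b of teeth is borderline, with mean error count m₁; the rest have mean 2.0. In one arm, borderline teeth are dropped after opening with probability q. Among those kept in that arm the borderline share is b(1 − q)/(1 − bq), so

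bias = (m₁ − 2.0) × [b(1 − q)/(1 − bq) − b].

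For b = 0.30, m₁ = 3.5:

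- q = 0.50: 1.5 × (0.15/0.85 − 0.30) = −0.19 errors
- q = 0.75: 1.5 × (0.075/0.775 − 0.30) = −0.31 errors (−0.305 before rounding)
- q = 1.00: 1.5 × (0 − 0.30) = −0.45 errors

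Type I error of the two-sided Wilcoxon test was simulated with Poisson counts and 50 per arm before drops. Repeated runs of 3,000 to 10,000 replicates gave:

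| b | m₁ | q | Type I error |
|---|---|---|---|
| 0.30 | 3.5 | 0.25 | about 5% to 6% |
| 0.30 | 3.5 | 0.50 | 7% to 8% |
| 0.30 | 3.5 | 0.75 | 11% to 12% |
| 0.30 | 3.5 | 1.00 | 18% to 20% |
| 0.10 | 3.5 | 0.50 | about 6% |
| 0.10 | 3.5 | 1.00 | about 6% to 7% |
| 0.30 | 2.5 | 0.50 | about 5% |

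A second model drops the hardest 10% or 20% of one arm, with error mean 2 and a latent correlation of 0.3 to 0.5 between difficulty and errors. It gives about 5% to 8% and 8% to 12% respectively. With zero correlation there is no inflation.

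**4. Visible trace.** With b = 0.30, expected drops are 50 × 0.30 × q = 7.5, 11.25 or 15 for q = 0.50, 0.75 or 1.00. That leaves about 42, 39 or 35 against 50.

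**The case against.** The documents lean toward eligibility first. The clinician form opens with the dropped/eligible block, finish line included, and only then asks for patient ID and impression group. Late opening gives a careful clinician time to measure while the arm is still concealed. The examination's place before preparation is inferred from paragraph order, and the form's finish-line box itself implies a later check. All of this stands: the plan leaves a gap open and does not prescribe exclusion after allocation. But form order is only a suggestion, and no text requires the block to be completed before opening.

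A reader might also infer that drops made after opening could never be detected. The documents do not support that. Envelopes are numbered in sequence, allocation is balanced in blocks of 4 within each clinic, and drop reasons are recorded. A drop after opening would leave an opened number without an analyzed patient, and one-sided drops would unbalance the arms. What is missing is a planned reconciliation, so detection is possible but not assured.

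Finally, the larger error rates need a high, wholly one-sided drop rate and a strong link between finish-line depth and errors. That is fair, and the range must start at no inflation. The study is also labeled exploratory, which lowers the stakes without removing them.

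**Conclusion.** The gap is real and worth closing. One eligibility criterion can be applied only after preparation, by the person who opens the envelope, and the plan neither orders the two acts nor says how a patient dropped after opening is counted. The technique-compliance rule is an explicit exclusion after allocation and belongs to the same problem.

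The size of any bias cannot be determined from the documents. Under the assumptions shown, type I error lies between about 5% and about 20%. The upper end requires 30% borderline teeth, mean errors of 3.5 against 2.0, and every borderline case dropped in one arm only. Which arm would lose cases is also an assumption.

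A reader might infer that the trial will be biased, or that the plan directs clinicians to screen with the arm known. Neither follows: a clinician who measures, completes the form and then opens the envelope complies fully with the text. The sample size calculation is unaffected.

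**What to change.** 1. Split the clinician form. The first part, covering every criterion including finish-line depth on the prepared tooth, is completed and signed before the envelope is opened. The second part starts with the impression group.
2. State in Methods that this order is mandatory and that a patient counts as randomized once the envelope is opened.
3. State in Statistical Analysis that the primary analysis keeps every such patient in the allocated arm.
4. Revise the sentence that admits an impression only if the technique protocol was followed, so that deviating impressions are left out only in a sensitivity analysis. Without this change, item 3 contradicts Methods.
5. Reconcile opened envelopes with analyzed patients and report the result by arm.

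The cost is a divided form, a few sentences in two sections and a simple envelope log. A few borderline or deviating cases stay in the primary analysis and may add some noise. No eligibility criterion or clinical procedure changes.

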More effective and efficient gingival displacement procedure can lead to clinically improved fixed restorations, less patient chair time, and less patient discomfort.

Materials and Methods: One hundred (100) patients will be recruited from the University of North Carolina (UNC) School of Dentistry (SOD). A stratified block randomization will be used to randomize patient to impression technique: Aquasil Ultra Cordless, Dentsply International using Aquasil Ultra Polyvinyl siloxane (PVS) impression material versus Dentsply International, gingival displacement cord (Ultrapak, Ultradent Products International) hydrated with aluminum chloride hexahydrate (Hemodent, Premier Dental Products Company). Stratification will be based on the clinic where treatment is provided (Dental Faculty Practice, Graduate Operative Dentistry, Graduate Prosthodontic Clinic), A block size of 4 within each stratum will be used to maintain a balanced allocation to impression group. Patient inclusion criteria include: 1) requires indirect restoration 2) probing depths 4mm or less. 3) No bleeding on probing. 4) finish line 0-1mm sub-gingival.

Specific Aims

The intent of this exploratory study is to compare two methods (cordless vs corded gingival displacement) currently used in clinical practice to displace sulcular tissues to facilitate an acceptable dental impression that accurately captures the prepared cervical finish line for the fabrication of indirect fixed prosthodontic restorations. The primary aims are to compare the two methods with respect to 1) the accuracy of the impression with respect to capturing the prepared cervical finish line for the fabrication of the indirect fixed prosthodontic restoration as assessed by two expert clinicians 2) the time required to prepare the impression and 3) the discomfort of the procedure as reported by the patient. Secondary aims are to estimate the effect of clinician experience (resident level vs faculty) and jaw of restoration placement (maxillary vs mandibular) on the outcomes of accuracy, time, and discomfort.

Significance

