- 2) Small diameter retraction cord, after it has been hydrated with Hemodent for 10 minutes, is tucked around the tooth in the space between it and its surrounding gum tissue. A second larger diameter retraction cord, also hydrated with Hemodent, will be placed over the first cord and tucked around the tooth. These cords will be left in place for a minimum of 8 minutes. These cords temporarily push the gum tissue back away from the tooth. (Before making the impression, the 2nd larger cord is removed, and the gums will stay back long enough for the impression material to seep around the tooth, thus allowing it to capture a copy of the entire tooth preparation.)
- 3) After a minimum of 8 minutes, the larger 2nd cord will be removed, and the tooth dried. Quickly, after confirmation of a dry field, the light body consistence impression material is syringed around the prepared tooth and across the occlusal surfaces of adjacent teeth.
- 4) An impression tray that has been filled with the heavy body consistency impression material is then placed over the arch of teeth, and gently pressed into place to ensure the teeth are completely covered with a uniform thickness of impression material. As the different impression material consistencies set, they fuse together into a single unit.
- 5) When removed from the mouth, the impression should contain a negative copy of both the prepared tooth and the teeth of that jaw.

Cordless Impression Procedure:

- 1) The prepared tooth is washed and dried, and assure hemostasis.
- 2) Apply B4 + surface optimizer.
- 3a) If 1 prepared tooth requiring an indirect restoration is being impressed, a single size (0.7mL) unit dose cartridge will be inserted into the digit power dispenser. If more than 1 prepared tooth requiring an indirect restoration is being impressed, a multi size (1.6mL) unit dose cartridge will be inserted into the digit power dispenser.
- 3b) Using the digit power dispenser, unit dose cartridge, and intrasulcular mixing tip, depress foot pedal and gently insert tip into the gingival sulcus of the prepared tooth, slightly apical to the preparation finish line. Material should flood the sulcus. Make sure to dispense material ahead of the intrasulcular tip, and completely around the prepared finish line, and then the tooth.

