Descriptive statistics for all study variables will be computed by impression group and used to summarize the procedural materials used in the impression and the outcomes. The primary outcomes are the number errors of the impression in the finish line; in the tray/material; and errors with gingival displacement/hemostasis (number of errors can range from 0 to 13), the time to complete the impression, and patient discomfort (range from 0 to 40). Since the outcomes are unlikely to be normally distributed, the Wilcoxon rank sum test will be used as the primary statistical test to assess whether the quality of impressions, time, or patient discomfort made with a cordless gingival displacement procedure is different than with a corded technique. To adjust for additional covariates [clinic providing care, jaw, procedural materials], Poisson regression will be used to assess the relationship between the primary outcomes and the covariates of interest, including impression group with a primary interest in estimation using confidence intervals.

The lack of historical data comparing the proposed outcomes between the two impression groups makes a sample size calculation difficult. For this exploratory study which is time constrained as a thesis project, a sample size calculation was done using an effect size which may be larger than the clinically meaningful effect size. A sample size of 30 in each group will have 80% power to detect a probability of 0.709 that an observation (number of total errors) in the Cordless group is less than an observation in the Corded group using a Wilcoxon (Mann-Whitney) rank-sum test with a 0.05 two-sided significance level.

Budget

Materials	Amount needed	Estimated costs
Aquasil Ultra Cordless Pneumatic Power Dispenser Units (3)	3 systems	Included in normal clinic treatment
Aquasil Ultra Cordless PVS material	Enough for 30 impressions + 10 for practice calibration.	Included in normal clinic treatment
Aquasil Ultra Cordless B4 Pre-Impression Surface Optimizer	Enough for 30 impressions + 10 for practice calibration.	Included in normal clinic treatment
Aquasil Ultra Cordless Ultrathin intra sulcular tips	Enough for 30 impressions + 10 for practice calibration.	Included in normal clinic treatment
Aquasil Ultra PVS materials (heavy and light body)	Enough for 60 impressions + 10 for practice calibration.	Included in normal clinic treatment

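### Randomisation is stratified by clinic but the primary Wilcoxon test pools the clinics, which gives up some power if clinics differ (efficiency, not validity)

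*Combined protocol and SAP*

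**What the plan says.** The Methods section sets up stratified block randomisation: "Stratification will be based on the clinic where treatment is provided", with three strata (the faculty practice and two graduate clinics) and blocks of 4.

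The Statistical Analysis section states that "the Wilcoxon rank sum test will be used as the primary statistical test" for all three primary outcomes: errors, time and discomfort. No stratified form is mentioned. Clinic appears in the next step: "To adjust for additional covariates [clinic providing care, jaw, procedural materials], Poisson regression will be used", with impression group in the model and the purpose given as "including impression group with a primary interest in estimation using confidence intervals".

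The sample size rests on the ordinary rank-sum test: 30 per group for 80% power at a two-sided 5% level. The effect is a probability of 0.709 that "an observation (number of total errors) in the Cordless group is less than an observation in the Corded group". The same paragraph concedes "an effect size which may be larger than the clinically meaningful effect size". Planned enrolment is 100, or about 50 per arm.

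**The concern.** The design balances the arms within each clinic, but the primary p-value does not use that balance. With blocks of 4 at 1:1, the arms in a clinic can differ by at most 2 patients, so differences between clinics can hardly contribute to the difference between arms. A pooled rank-sum test still counts those differences as noise. Its reference variance is then too large, and the test becomes conservative.

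Clinic differences are plausible on the plan's own terms. One stratum is a faculty practice and two are resident clinics, the Specific Aims section makes clinician experience a secondary aim for all three outcomes, and the analysis section lists clinic as a covariate. What is at stake is power for errors and discomfort, mainly for effects smaller than the design effect.

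**Working it through.** **Reproducing the stated figure.** Inputs from the Statistical Analysis section: p = 0.709, two-sided α = 0.05, power 80%. Noether's formula with 1:1 allocation gives

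N = (1.960 + 0.842)² / [12 × 0.25 × (0.709 − 0.5)²] = 7.849 / 0.1310 = 59.9,

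that is 29.95, or 30 per group. At N = 60 power is Φ(√180 × 0.209 − 1.960) = 80.1%. At N = 100 it is Φ(√300 × 0.209 − 1.960) = 95.2%. The plan's figure is correct for the pooled test.

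**The comparison.** In clinic k, with n_k patients of whom m_k are cordless, let W_k be the cordless rank sum within the clinic, E_k = m_k(n_k + 1)/2, and V_k its tie-corrected variance. The van Elteren statistic is

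Z = Σ (W_k − E_k)/(n_k + 1) ÷ √[Σ V_k/(n_k + 1)²].

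It was compared by simulation with the tie-corrected pooled Mann-Whitney test (20,000 or 40,000 replicates, two-sided 5%). The documents give no clinic sizes or clinic differences, so all of those below are assumptions. Clinics are listed faculty practice first, and each pair of powers is pooled v stratified.

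**Errors, 50 per arm (16/18/16 by clinic), Poisson counts, rate ratio 0.67**

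| Corded mean errors by clinic | Pooled power | Stratified power | Pooled type I error |
|---|---|---|---|
| 2 / 2 / 2 | 69% | 69% | about 5% |
| 1.5 / 2 / 2.5 | 67% | 68% | 4.3% |
| 1 / 2 / 2 | 56% | 60% | 3.5% |
| 1 / 2 / 3 | 57% | 67% | 2.4% |

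Stratified type I error was 4.6% to 5.4% in the null scenarios run.

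**Unequal clinics.** If the faculty practice is small (4 or 6 of 50 per arm), the gaps in the last three rows become about 1, 1 to 2, and 4 to 5 points. If it is the largest (30/14/6), they become about 1, 5 and 9 points.

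**Is the stated power missed?** The plan defines 0.709 between whole groups. With that pooled probability held at 0.709 and 30 per arm (10/10/10):

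| Outcome and clinic pattern | Pooled | Stratified |
|---|---|---|
| Normal, no clinic difference | 82% | 82% |
| Normal, 0.5 SD between adjacent clinics | 84% | 87% |
| Normal, 1 SD between adjacent clinics | 88% | 96% |
| Counts 2 / 2 / 2 | 85% | 84% |
| Counts 1.5 / 2 / 2.5 | 86% | 87% |
| Counts 1 / 2 / 2 | 87% | 89% |
| Counts 1 / 2 / 3 | 88% | 91% |

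The planned test keeps at least 82% throughout, and 96% or more at 50 per arm. It falls below 80% at 30 per arm only if 0.709 is read as a within-clinic effect: 77% v 82% at 0.5 SD and 62% v 82% at 1 SD. The between-group probability is then about 0.69 and 0.66, which is not what the plan defines.

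**Discomfort, 50 per arm, mean total 9 v 11, by cordless clinic means.** 9/9/9: 73% v 72%. 8/9/10: 71% v 72%. 7.3/9/11.3: 65% v 72%. Each total is the sum of four 1-10 ratings with a patient random effect, and treatment acts on the last two ratings only.

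**Time, 30 per arm, clinics up to 40% apart.** Cordless half as long: 100% v 100%. Cordless 30% shorter: 99% v 99%. The Methods section says of the corded arm, "These cords will be left in place for a minimum of 8 minutes". If the recorded time includes that wait, either test should detect the difference.

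**Effects that vary by clinic.** With error rate ratios of 0.5/0.67/0.84, the reverse, or 1/0.6/0.6 at 50 per arm, stratifying changed power by −0.5 to +15 points.

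**The case against.** The strongest reply is that nothing here is an error. The primary test and the power calculation name the same ordinary rank-sum test, validity is intact, and the stated power is met on the plan's own definition. The trial is exploratory, and its estimates and intervals already adjust for clinic. Clinicians are trained and calibrated and work from laminated protocols, so clinics may differ little. The gap is then 0 to 1 point, and one near 10 points needs a threefold spread in mean errors. For time there is nothing to gain. The downside can also exceed 1 point: with clinic totals of 32/20/8 and no clinic difference, the stratified test lost 1.5 points (82.3% v 80.9% before rounding of the difference).

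All of this stands, and it limits the point to efficiency. It does not remove it. The p-value named as primary still ignores a factor that the design controls. The plan itself doubts that the clinically meaningful effect is as large as 0.709, and at a 33% error reduction the pooled test has only 56% to 69% power with 50 per arm and near-equal clinics. There, 4 to 10 points are worth having in exchange for a possible loss of 0.5 to 1.5.

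**Conclusion.** The point holds as a modest, conditional loss of efficiency. If clinics are alike, pooling costs nothing. If they differ, the pooled test is conservative and, for errors at a 33% reduction with 50 per arm, loses about 1 point under mild differences, 1 to 5 if only the faculty practice differs twofold, and 4 to 10 under a threefold spread, depending on clinic sizes. For discomfort the loss reaches about 7 points in the widest case tried, and for time it is negligible. These sizes rest on assumed clinic means, clinic sizes and outcome distributions, because the documents supply none. Neither inflated type I error nor a shortfall from the stated 80% power is claimed.

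**What to change.** Before outcome data are reviewed, name the van Elteren test (Wilcoxon stratified by clinic) as the primary test for errors and discomfort, and for time for consistency. Keep the unstratified Wilcoxon as a sensitivity analysis and leave the clinic-adjusted Poisson model as planned.

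This takes one sentence in the Statistical Analysis section. A short clause in the sample-size paragraph, saying that 30 per group was calculated for the unstratified test, would keep the two consistent. Clinic is already on the treating clinician's form, so data collection, conduct and sample size do not change. The price is about 0.5 to 1.5 points of power if the clinics prove alike. The choice should be fixed in advance, because choosing between the two tests after seeing results would be data-driven.
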